4.3 Recruitment materials

See details of procedure in section 4.2

- 1) Options Pre-Note Initial Recruitment Letter
- 2) Options Phone Script Baseline Invite
- 3) Options Reminder Email for Baseline Participation
- 4) Options Phone Script for Baseline Survey
- 5) Options Reminder Letter for Baseline Participation
- 6) Options Phone Reminder Script for Baseline Survey
- 7) Options 1 Month Followup Survey Email Mail Invite
- 8) Options 1 Month Followup Survey Reminder Email
- 9) Options 3 Month Followup Survey Email Mail Invite
- 10) Options 3 Month Followup Survey Reminder Email
- 11) Options Followup Reminder Call Script
- 12) Options Followup Survey Text Message Reminder
- 13) Options Thank You Letter for Study
- 14) Options Collateral Contact Call Script
- 15) Options Collateral Contact Email Mailed Letter

4.4 Eligibility/screening of subjects

Patients will be pre-screened following the inclusion and exclusion criteria listed in sections 3.1 and 3.2 of this protocol by the PSHMC Dermatology Research Nurse Coordinator who has clinical access to this patient population. Subjects will then give verbal consent to be screened over the phone for eligibility for this research study for items not able to be determined from clinical access.

5.0 Consent Process and Documentation

5.1 Consent Process

5.1.1 Obtaining Informed Consent

5.1.1.1 Timing and Location of Consent

If a patient expresses interest in participating when they are called to be invited over the phone (or when they contact us), they will be verbally consented to be screened for the research study (see phone scripts for consenting language).

Research assistants will then approach participants to obtain informed consent when they arrive in the dermatology clinics at PSHMC and State College after they check in for their appointment. The research assistant will escort the patient to a private area where the informed consent process will take place. The consent form will be read and reviewed in its entirety, all questions will be answered prior to the subject signing for participation. If patients agree to participate, they will then sign the informed consent form and provided a copy.

Additionally, at the beginning of every online survey (as well as paper-based copies), it will include the text that states "By completing the following survey you are agreeing to take part in this research study. If you have any questions about the

survey or your participation, please contact project coordinator, [name], at [contact] or [contact]".

For participating physicians: Those physicians who agree to participate in the research will give verbal consent after reviewing the Summary Explanation of Research provided by a member of the research team during the scheduled training (intervention) or prior to patients being recruited (control).

5.1.1.2 Coercion or Undue Influence during Consent

Study procedures will be fully explained, all critical study information will be disclosed, voluntariness will be emphasized as well as the fact that no care will be denied regardless of the subject's decision. Subjects will be told they do not have to participate in the research. They will be told that whether or not they agree to participate in the study, their current or future care at the PSHMC will not be affected by their decision.

For physician subjects, they will be told they do not have to take part in the research and that their educational and employment status will not be affected in any way by their decision.

5.1.2 Waiver or alteration of the informed consent requirement

We are requesting a waiver of informed consent so that the Hershey coordinator/team can review clinic schedules for recruitment purposes. This waiver will minimize the possibility of subjects being contacted who do not qualify for the research based on information available in their medical record.

5.2 Consent Documentation

5.2.1 Written Documentation of Consent

Written informed consent will be obtained from all participants in a private area of the clinic prior to their scheduled appointment. The consent form will be read and reviewed in its entirety with the subject, all questions will be answered prior to the potential subject signing for participation. Both the subject and the investigator obtaining informed consent will sign, date and time the consent document.

The participant will receive a signed/dated copy of the consent documentation for their records.

A copy of the signed consent form will not be added to the subject's medical record.

5.2.2 Waiver of Documentation of Consent

Verbal consent will be obtained to screen potential participants for eligibility. This waiver will minimize the possibility of subjects being approached in the clinic who do not qualify for the research based on information available in their medical record or able to be screened for via the telephone.

5.3 Consent – Other Considerations

5.3.1 Non-English Speaking Subjects

Not Applicable – Participants will not be non-English speaking

5.3.2 Cognitively Impaired Adults

5.3.2.1 Capability of Providing Consent

Not Applicable - Participants will not be cognitively impaired

5.3.2.2 Adults Unable To Consent

Not Applicable

5.3.2.3 Assent

Not Applicable

5.3.3 Subjects who are not yet adults (infants, children, teenagers)

5.3.3.1 Parental Permission

Not Applicable – Inclusions criteria states that participants must be at least 21 years of age.

5.3.3.2 Assent

Not Applicable

6.0 HIPAA Research Authorization and/or Waiver or Alteration of Authorization

6.1 Authorization and/or Waiver or Alteration of Authorization for the Uses and Disclosures of PHI

Check all that apply:

- Authorization will be obtained and documented as part of the consent process.
- Partial waiver is requested for recruitment purposes only (Check this box if patients' medical records will be accessed to determine eligibility before consent/authorization has been obtained)

imes

- Full waiver is requested for entire research study (e.g., medical record review studies)
- Alteration is requested to waive requirement for written documentation of authorization

6.2 Waiver or Alteration of Authorization for the Uses and Disclosures of PHI

6.2.1 Access, use or disclosure of PHI representing no more than a minimal risk to the privacy of the individual

6.2.1.1 Plan to protect PHI from improper use or disclosure Information is included in Section 10 of this protocol.

6.2.1.2 Plan to destroy identifiers or a justification for retaining identifiers The patient permission for the use, storage, and sharing of their health information will expire upon completion of the research study. At that time, the identifying research information will be destroyed.

6.2.2 Explanation for why the research could not be practicably be conducted without access to and use of PHI

We will be conducting the study in dermatology clinics and will be contacting participants via mail, email, and/or phone for recruitment purposes. We will need the names of participants in order to know who was deemed eligible by clinic nurses, and as age is an inclusion criteria, we will need access to age. However, until the patients agree to participate in the study via the phone screening or contact PSU researchers directly, the

PSHMC Dermatology Research Nurse Coordinator/Hershey team will be the only ones with access to this information.

6.2.3 Explanation for why the research could not practicably be conducted without the waiver or alteration of authorization

The waiver of authorization is required to screen for eligibility.

6.3 Waiver or alteration of authorization statements of agreement Not Applicable

7.0 Study Design and Procedures

7.1 Study Design

This study will use a longitudinal design to compare the effect of the ABC intervention on the intervention group versus the control group receiving TAU. Participants will not be randomized to a group. Instead, patients who meet eligibility criteria at PSHMC will be invited to participate at the intervention site, and current patients who meet eligibility criteria at the clinic in State College will be invited to participate at the control site.

7.2 Study Procedures

Subjects will be recruited from two sites: 1) Penn State Hershey Medical Center Clinic in Hershey (PSHMC), which will serve as the intervention site where patient participants will receive the ABC interventions, and 2) Penn State Medical Group in State College (State College), which will serve as the control site where patient participants will receive TAU.

- 1) Participation will begin when participants are screened for eligibility over the phone.
- 2) Participation will continue for subjects when they arrive at either PSHMC or State College for an appointment with a participating physician that will include a skin check (either annual full body skin check or suspicious lesion) or Mohs surgical procedure (please see the recruitment section for a step-by-step process of how eligible participants will be obtained). A skin check involves the physician checking the patients' skin for any growth or mark that could potentially become cancerous. Patients at the control site will be receiving TAU for their skin check; patients at the intervention site will receive a normal skin-check, combined with the ABC-intervention (see uploaded information sheet). The audio recordings which will be done at both the control and intervention sites for all participants will be used to compare the information patients receive from their doctor during the course of a skin check.
- 3) Participants will be asked to arrive 25 minutes prior to their appointment so the informed consent process may take place prior to any study related procedures being conducted. After they check in, they will be greeted by a research assistant in the waiting room and directed to a private area within the clinic. The research assistant will be accessible while the participant completes the survey to answer questions that may arise. The baseline survey will assess demographic information, history of skin cancer, UV risk behaviors, perceived risk of skin cancer, dermatologist communication, attitudes about sun protection behavior, self-efficacy about sun protective behaviors, etc. (Please refer to Measures document for full questionnaire).
- 4) As part of the surveys, participants will be asked to provide the contact information of a friend or relative that we could contact in the event that we are unable to locate the individual for the 1-month and 3-month follow-up surveys. Phone and email/letter scripts are included in the recruitment documents. We will attempt to call the "collateral contact" up to 2 times, and then will send a letter or email if we cannot reach them by phone. Participants will be reminded of the following when they log on to the survey: "By completing the following survey you are agreeing to take part in this research study. If you have any questions about

the survey or your participation, please contact project coordinator, [name], at [contact] or [contact]".

- 5) The patient will then proceed to their appointment with a dermatologist. At the intervention site, the provider who has been trained to deliver the ABC intervention will do so during the skin exam. During the appointment at the intervention site, providers will provide their patients with a handout (as a small card and/or magnet) which summarizes what they discussed during the appointment regarding sun protection (CURE Method Tips – see uploaded document). At the control site, patients will receive TAU, with no ABC intervention. All patient participant appointments are to be audio recorded and by consenting to the study, patients are consenting to be audio recorded. A research assistant will accompany the patient into the exam room to audio record the visit. Only providers who have taken the appropriate training will have patients identified to participate in this study (intervention). Providers at both the intervention and control sites will be consented prior to any audio recordings being done, as explained in section 5.1.1. Research assistants will later listen to and code the data to determine if the components of the ABC intervention were delivered with fidelity. Control sessions will be recorded and coded using the same criteria to document those patients who did not receive elements of the ABC intervention. The recordings will be coded with the patient's study number and will be destroyed per PSHMC IT Security Group policy as soon as data is coded from their analysis. The participant and the provider will be reminded prior to the recording to not use names or other identifying information during the recording.
- 6) At 1-months and 3-months following this appointment, the first (1 month) and second (3 months) follow-up surveys will be sent out, via email to complete online to allow participants to complete at home. Participants can request mailed, paper-based surveys if they do not want to complete the online version of the survey. A cover letter and paper-based surveys will be mailed to participants' homes along with prepaid return envelopes. In an email, participants will be instructed to complete the survey online (or, if the participant requested a mailed paper-based survey, they will be instructed via mailed letter to mail back the paperbased survey to the investigator's office in the enclosed pre-paid envelopes). The 1-month and 3-month follow-up surveys will be almost identical to the baseline survey (minus the screening items, background item, and physician communication item, as indicated in the measures document), and each should take about 5-10 minutes to complete. Participants will receive a \$25 Walmart gift card, Target gift card, or Amazon electronic gift card for completing each survey, totaling \$75 if they complete all 3 surveys. Participants will be paid for the baseline survey after completion of the visit, and the two follow-up surveys will be paid at the end of the study (that is, after the 3-month follow-up survey). If they do not complete all surveys they will be compensated for the ones they do complete. Participants will be asked during the screening call which payment option they would like, so that we can have the appropriate option in clinic, and if they do not complete one of the follow-up surveys, we will have their payment option on file.

Note: Dermatologists from the intervention site will undergo 1 session of training to deliver the ABC intervention. This will take place during the rescheduled weekly journal club meeting, which will take place in the evening and will require no additional time. 1) The first component of training will involve learning to deliver each of the 6 components of the intervention. Patient interactions will be demonstrated by the study staff. 2) The second component will involve role plays. The physicians will practice implementing the intervention on research assistants who will pose as mock patients. 3) The third component will involve supervision and feedback. Drs. [name] and [name] will observe the physicians while they deliver the ABC intervention to patients. They will then provide feedback privately. Up to 10 providers from the departments of dermatology at each site will be selected to perform the skin exams, based on their availability.

Physicians at the control site will deliver TAU to their patients, and will not undergo the training and supervision.

7.3 Duration of Participation

Patient participants will be involved in the study for up to 4 months. The baseline visit in clinic will take approximately 25 minutes longer than their scheduled appointment, which lasts on average 15 minutes (they are asked to arrive 25 minutes early to complete the consent and baseline survey). Each post- survey will take 5-10 minutes to complete. Participants will complete a baseline assessment, and subsequent 1-month and 3-month post-surveys.

Their participation will last up to 60 minutes (inclusive of their scheduled dermatologist appointment) over a 4 month period.

Dermatologists at the intervention site will be involved from the beginning of their training through the end of baseline data collection, approximately 8-10 weeks (April-May 2016 & 2017). Dermatologists at the control site will be involved only during baseline data collection, approximately 8-10 weeks (April-May 2016 & 2017).

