16.0 Number of Subjects

The total maximum number of participants to be enrolled is 894.

The number of patient participants that will be contacted (up to 874) is much larger than the number we intend to enroll (227 – including both Cohort 1 and Cohort 2) (27 enrolled in Cohort 1 between Intervention and Control; 200 intended to enroll in Cohort 2 – 100 intervention, and 100 control). Based on the response rate of the first cohort in Spring 2016, we anticipate a 26% overall response rate, resulting in 200 individuals (for cohort 2) who agree to participate. However, due to uncertainty on the

overall response rate, participants will be invited in chunks and once we hit our target enrollment, we will stop recruiting. Additionally, we will enroll up to 20 providers (up to 10 from the control site and up to 10 from the intervention site).

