25.3 Aim 1: Evaluate efficacy of the ABC intervention

[name] (Co-I) will conduct all outcome analyses in order to avoid any bias. First a 2 (Group: ABC vs. Controls) x 3 (Time: baseline, 3 & 6 mo. follow-up) Mixed ANOVA will be conducted to test the intervention on a given outcome variable (e.g., use of sun protection). First, we expect to observe a main effect of Group with the highest reports of sun protection (and lowest reports of UV risk behaviors) occurring in our ABC condition. Second, we anticipate observing a Group x Time interaction with no differences between the groups at baseline but differences (lower risk in the ABC group) at each of the follow-ups. He will also assess the scientific and clinical significance of the effects utilizing the magnitude estimation approach described by Jaccard. Specifically, statistical significance refers to the case when the null hypothesis is rejected, whereas magnitude estimation approaches emphasize the size of the effect. To utilize magnitude

estimation approaches, the researcher must specify an a priori effect size that differentiates a trivial effect from a meaningful effect. If the effect size observed is less than the criterion for meaningfulness, then the result is deemed nonsignificant, even if the null is rejected. We will use Cohen's d statistic to assess clinical significance of the main effects and interactions. We will define an effect as clinically and statistically significant to the extent that the d is greater than or equal to .20.

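### Visit dates are neither balanced between the two non-randomized clinics nor adjusted for, so a seasonal difference between arms would pass into the Group x Time test.

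*Combined protocol and SAP*

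**What the plan says.** Protocol 7.1 and 7.2 assign arm by clinic, without randomization: Hershey delivers ABC and State College delivers usual care. For Hershey, 7.3 states: "Dermatologists at the intervention site will be involved from the beginning of their training through the end of baseline data collection, approximately 8-10 weeks". For State College: "Dermatologists at the control site will be involved only during baseline data collection, approximately 8-10 weeks (April-May 2016 & 2017"). The months are the same for both.

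On training, 7.2 says: "Dermatologists from the intervention site will undergo 1 session of training to deliver the ABC intervention". It adds: "This will take place during the rescheduled weekly journal club meeting, which will take place in the evening and will require no additional time". It also says: "Only providers who have taken the appropriate training will have patients identified to participate in this study (intervention"). The supervision component takes place while physicians see patients. For Spring 2017, section 4.2 describes a booster and names only that supervision component.

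On pacing, section 16.0 says: "participants will be invited in chunks and once we hit our target enrollment, we will stop recruiting". Section 4.2 sets the stop at 200 in total, about 100 per site, for the 2017 cohort; 27 patients were enrolled in 2016. No section ties the two clinics' invitations to the same weeks.

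Follow-up is timed from each patient's own appointment (7.2). SAP 25.3 analyses each outcome with a Group by Time mixed ANOVA and states: "we anticipate observing a Group x Time interaction with no differences between the groups at baseline". It names no covariate for survey date and no factor for cohort.

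**The concern.** The outcomes are UV protective and UV risk behaviours. How often people use sunscreen or get burned plausibly depends on the time of year. Baselines are spread over roughly two spring months, so at each survey patients are at different points of the season. If one clinic's visits come later on average, its patients report under different conditions at every survey.

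Group x Time is the contrast least exposed to fixed differences between the clinics, so it carries most of the inferential weight. It removes a constant clinic difference, and also a linear seasonal trend. It does not remove a season that climbs in April-May and levels off in July-August. The later arm starts higher on the slope and has less left to climb, so the two arms change by different amounts with no intervention effect. Nothing in the design balances dates, and nothing in the model corrects for them.

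**Working it through.** **Window.** 1 April to 31 May is 61 days; 61/7 = 8.71 weeks, which agrees with the stated 8-10 weeks. On the 1- and 3-month schedule, follow-up then falls in May-June and in July-August.

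**How large an offset do the documents imply?** Assume even enrolment in a shared window. If one clinic starts L weeks late, its mean visit date shifts by L/2 weeks.
- One evening session: L of about 0-1 week, so a mean shift of 0-0.5 week.
- First-time training, then the letter route (2-4 weeks before the visit, section 4.1): L up to about 4-5 weeks, so a shift of 2-2.5 weeks. If this applies to 2016 only, the pooled shift is at most 2.5 x 27/227 = 0.30 week.
- In 2017 (200/227 = 88% of planned patients) only supervision during patient visits is described, which need not delay enrolment.
- Unpaced chunks: the documents set no limit on the offset in either direction.

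**Bias formula.** Let m(t) be the seasonal mean on day t of the year, b the mean baseline day of one arm, and o the number of days by which the other arm is later. With no intervention effect,

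bias = [m(b+91+o) - m(b+o)] - [m(b+91) - m(b)].

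If m is linear with slope s, this is s x 91 - s x 91 = 0. A linear season cancels.

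**Assumed curve.** m(t) = A cos(2 pi (t - 196)/365), peaking on day 196 (mid-July), with trough-to-peak 2A = 0.5 or 1.0 SD and b = day 105 or 115 (mid to late April). The documents give no seasonal amplitude, so this range is an assumption.

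Worked case: 2A = 1.0, b = 115, o = 14.
- Earlier arm: m(115) = 0.088, m(206) = 0.493, change 0.405.
- Later arm: m(129) = 0.203, m(220) = 0.458, change 0.255.
- Bias = 0.255 - 0.405 = -0.150 SD.

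**Rejection rate.** With 227/2 = 113.5 per arm and an assumed baseline to follow-up correlation of 0.5, SE = sqrt(2 x 2(1 - 0.5)/113.5) = 0.133 SD. For the worked case z = 0.150/0.133 = 1.13, and the two-sided .05 rejection probability is P(Z > 1.96 - 1.13) + P(Z < -1.96 - 1.13) = 0.20.

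| Mean offset | Bias in 3-month change (SD) | Rejection with no true effect |
|---|---|---|
| none | 0 | 5% |
| 0.5 week | 0.02-0.04 | 5.2-5.8% |
| 1 week | 0.03-0.07 | 5.7-8.5% |
| 2 weeks | 0.07-0.15 | 8-20% |

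**Direction.** The later arm always shows the smaller rise. If Hershey is later, this counts against ABC on protective behaviours (the primary endpoint in 1.2) and in favour of ABC on outcomes such as sunburn. If State College is later, both signs reverse.

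**Schedule.** Sections 4.2, 7.2 and 7.3 place follow-up at 1 and 3 months; 1.1 and SAP 25.3 place it at 3 and 6 months. The figures above are for 3 months. For 6 months, replace 91 by 182. With 2A = 1.0, b = 105 and o = 14, the earlier arm changes by 0.002 - 0.002 = 0 and the later arm by -0.117 - 0.121 = -0.239, so the bias is about -0.24 SD. At 3 months the same inputs give -0.134 SD. The choice of schedule therefore matters to the size.

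**The case against.** A reader might infer from 7.3 that training pushes Hershey's enrolment later, so that the arms do fall at different points of the season. The documents do not support that. Section 7.3 says how long dermatologists take part and is not an enrolment calendar; it gives both clinics the same months. Training is one evening session, and supervision happens during patient visits. The rule that providers be trained before patients are identified does not say that the 2017 booster must come first, and providers trained in 2016 may already qualify. One coordinator role reviews schedules at both sites (4.1), and nothing suggests that invitations run in sequence.

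A reader might also be tempted by larger figures. A 3-week difference in mean date would give 0.10-0.23 SD and 12-41% rejection under the same assumptions. With even enrolment it would need one clinic to start about 6 weeks late in a window of about 9, and no section implies that. On protective behaviours with Hershey later, nearly all of those rejections would be against ABC, so they cannot be read as a risk of false benefit on the primary endpoint.

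These objections stand, and they limit the training route to about half a week. They do not answer the rest: the clinics are unpaced, the stopping rule lets one fill earlier than the other, and the model would neither show nor correct a difference.

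**Conclusion.** The point holds as an uncontrolled risk with a cheap remedy; it is not a demonstrated bias. Training alone is close to negligible. An offset of 1-2 weeks from unpaced recruitment would consume roughly one sixth to three quarters of the SAP's d = .20 threshold (0.03/0.20 to 0.15/0.20), with a sign that depends on which clinic is later and on the outcome. The size rests on the assumed cosine season, its mid-July peak, the 0.5-1.0 SD range, the correlation of 0.5 and the 3-month follow-up. With equal mean dates, or a season that is linear over the study months, the bias in change is zero. Confidence is high that the plan has no balance or adjustment for date, and moderate at best on how much this matters.

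**What to change.** In SAP 25.3, fit Aim 1 as a mixed model that adds calendar date and cohort (2016 or 2017). Date can enter as baseline visit date with its interaction with Time, or as linear and quadratic day of year of each survey. Fix the form before the outcome data are examined. Report the distribution of baseline and follow-up dates by arm, so that readers can see whether an offset arose. In 4.2 and 16.0, where feasible, release invitation chunks to both clinics in the same weeks. Making the faster clinic wait is not advised as a rule, because it puts the target of 200 at risk in an 8-10 week window. Nor should the 2017 booster be required before enrolment, since it consists of observing delivery to patients. Reconcile the 1- and 3-month schedule (4.2, 7.2, 7.3) with the 3- and 6-month schedule (1.1, 25.3), because they put follow-up in different seasons.

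The cost is SAP wording and a few degrees of freedom; the survey and visit dates should already be on file. Two limits should be stated. The adjustment relies on the clinics' dates overlapping, and it does not remove the confounding of arm with clinic.
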